Variables to be measured

TES HT examinations should be performed within 24 hours before or after the CT examination.

Systematic errors - bias

Systematic errors that may occur during the study are mainly related to the marked movement of the patient, who should avoid abrupt movements throughout the scan in order to reduce motion artifacts.

Patient selection

Patient inclusion criteria:

Group 1:

- age over 18 years
- acquisition of informed consent
- Patients referred to the emergency department for mild head injury

Group 2:

- age greater than 18 years
- acquisition of informed consent
- Patients afferent to the emergency department not for head trauma and not in a critical condition, with one of the following neurological symptoms:

- Syncope
- Spatial disorientation and/or loss of balance
- Speech disturbance and/or facial hemi-paresis
- Visual alterations
- Lack of memory and/or confusional state

Exclusion criteria for both cohorts:

- age less than 18 years
- pregnant women
- Metal plates or metal prostheses installed in the skull cap
- severe head trauma and/or with extensive lacerated contused areas
- patient in critical condition
- skull theca fracture
- failure to sign informed consent

The TES-HT device cannot be used in cases of metal plates or metal prostheses installed in the skullcap because their presence alters the outcome of the TES HT100 examination.

Number of patients expected to enroll

Considering that it is intended to prove the primary hypothesis that TES HT 100 succeeds in achieving a sensitivity and specificity of 90% when comparing to the outcome of the CT scan report, an AUC of 0.90 is obtained, a value indicative of its excellent reliability. Assuming that TES HT100 meets this performance, a sample size of about 384 subjects is needed to obtain a maximum error of 3% on the confidence interval in the 95% two-tailed test on AUC. In other words, the target AUC and sample size should allow 95% confidence that the AUC is within the range [0.87;0.93]. Given a 10% drop-out rate, a sample size of 425 subjects for each patient cohort is considered necessary. Although the sample size calculation was performed as was previously explained, we believe it is fair to consider, in the case where there is a large imbalance between positive and negative outcomes, a small adjustment on the precision of the AUC estimate. Specifically, we will consider a precision of 0.02 instead of 0.03.

Point of enrollment

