- 2) **Low risk to the patient** - The device does not emit ionizing radiation (as with CT scanning) and emission levels are well below reference limits.
- 3) **Short scan duration** - The duration of one measurement is 4 minutes.
- 4) **Small size and easily transportable** - The small size makes TES HT a device that can be used in all emergency situations and in places where rapid transport to a First Aid Center is difficult.

Thus, the device demonstrates positive cost-benefit and timely and beneficial results.

Statistics

To evaluate the performance of the device, statistical sensitivity and statistical specificity will be calculated. Statistical sensitivity indicates the device's ability to correctly identify positive cases, i.e., patients with brain injury (prior or post injury) and/or structural alteration of brain tissue. Statistical specificity indicates the ability of the device to correctly identify negative cases, i.e., patients with no brain injury (new or previous) and no structural alteration of brain tissue. All TES HT examinations will be compared with the CT scan report, which will sanction the actual presence or absence of structural alterations of brain tissue. Comparison criteria such as Receiver Operating Characteristic-Area under curve (ROC-AUC), sensitivity and specificity will be used as statistical validation tools. To this end, it is intended to demonstrate the primary hypothesis regarding a diagnostic performance of TES HT 100 not less than 90% ROC-AUC compared to the outcome of the CT report, while maintaining sensitivity and specificity of at least 80%. The minimum threshold of 90% is indicative of excellent instrument reliability.

To calculate the statistical sensitivity and specificity, the following data will be used:

	Brain injury present	Brain injury absent
Positive test	TP (True Positive)	FP (False Positive)
Negative Test	FN (False Negative)	TN (True Negative)
Total	TP+FN	FP+TN

- Number of true positive cases (TP): number of patients with brain injury (prior or posttrauma) and/or structural alteration of brain tissue identified

correctly by the device and confirmed by CT scan

- Number of false-negative (FN) cases: number of patients with brain injury (prior or posttrauma) and/or structural alteration of brain tissue not identified by the device but confirmed by CT scan

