- Number of false-positive (FP) cases: number of patients without brain injury (prior or posttrauma) and/or structural alteration of brain tissue identified as positive by the device but confirmed as negative by CT scan
- Number of true negative cases (TN): number of patients without brain injury (prior or posttrauma) and/or structural alteration of brain tissue identified correctly by the device and confirmed by CT scan

Statistical sensitivity is calculated as $TP/(TP+FN)$, while statistical specificity is calculated as $TN/(TN+FP)$. It will also be calculated:

- the positive predictive value: probability that the disease is present when the test is positive calculated as $TP/(TP+FP)$
- the negative predictive value: probability that the disease is not present when the test is negative as $TN/(FN+TN)$

Specificity and sensitivity will also be evaluated for different subgroups of patients enrolled such as:

- Young patients <65 years old
- Elderly patients >65 years old
- Patients with or without prior injuries or who have undergone brain surgery
- Patients with or without neurodegenerative diseases.

An interim analysis is planned for the respective cohorts of study patients when the thresholds of 150 and 300 patients enrolled in each cohort are reached.

Quality assurance, control procedures, data management and record keeping

Subject data will be recorded in a secure electronic data capture (EDC) with limited access. All changes made to clinical data will be captured in an electronic *audit trail* and available for review by the Sponsor or its representative. The software and database associated with data acquisition and storage have been designed to meet compliance with applicable laws and regulations, regarding data processing. Data collected on study subjects are in accordance with the ICH/GCP Guidelines valid in the European Union. Records must be kept for ten years after the completion of the device trial.

Each data collected should contain:

- ID of the examination performed on TES-HT (ID generated by TES-HT for each examination);
- Location where the examination takes place (emergency district or other), time, date and operator.
- Anonymous patient history

Deviations from the clinical evaluation plan

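### The protocol sets out to demonstrate an AUC of at least 0.90, but sizes each cohort for precision only, at an assumed AUC of exactly 0.90

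*Protocol*

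**What the plan says.** Two sections of the protocol use the value 0.90, in different roles.

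- **Statistics.** The aim is confirmatory in wording: "it is intended to demonstrate the primary hypothesis regarding a diagnostic performance of TES HT 100 not less than 90% ROC-AUC", together with sensitivity and specificity of at least 80%. The same paragraph treats the figure as a floor: "The minimum threshold of 90% is indicative of excellent instrument reliability".
- **Number of patients expected to enroll.** Here 0.90 is the assumed truth. The device is taken to succeed in "achieving a sensitivity and specificity of 90% when comparing to the outcome of the CT scan report, an AUC of 0.90 is obtained". The calculation then runs: "Assuming that TES HT100 meets this performance, a sample size of about 384 subjects is needed". The purpose given for that number is precision, namely "to obtain a maximum error of 3% on the confidence interval in the 95% two-tailed test on AUC". The stated consequence is that "the target AUC and sample size should allow 95% confidence that the AUC is within the range [0.87;0.93" (closing bracket follows in the text). After a 10% allowance for drop-out, each cohort has 425 patients.

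The protocol gives no power, no assumed AUC above 0.90 for sizing and no acceptance limit below 0.90. It does not say whether the point estimate or the confidence interval decides.

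**The concern.** A minimum to be demonstrated and an expected value serve different purposes in a design. A trial can show that a parameter is not below a minimum only if the true value is expected to lie far enough above it for the sampling error to fit in between. Here that distance is zero. The interval the protocol plans for reaches down to 0.87, so the expected result does not exclude values below the stated minimum.

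This affects how the result can be reported. If the device performs as the sizing assumes, the trial will give a reasonable estimate near 0.90 and will usually be unable to support the sentence that the AUC is not less than 0.90. The protocol says the purpose of the investigation is to commercialize the device, so the primary claim should be one that the design can carry.

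**Working it through.** **1. Reproduce the sample size.** Inputs from the sample size section: p = 0.90, half-width d = 0.03, two-sided 95% (z = 1.96).

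n = z² p(1 − p) / d² = 1.96² × 0.90 × 0.10 / 0.03² = 384.2, against the stated 384. For drop-out, 384 / 0.90 = 427 and 384 × 1.10 = 422; the stated 425 lies between them. The figure reproduces as a pure precision size, and no power term enters it.

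**2. Chance of success at the sizing assumption.** The implied standard error is 0.03 / 1.96 = 0.0153.

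- Interval rule: the lower limit exceeds 0.90 when the estimate exceeds 0.90 + 1.96 × SE. With true AUC 0.90 this has probability 1 − Φ(1.96) = 2.5%.
- Point-estimate rule: P(estimate ≥ 0.90) = 50%.

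The SE cancels from both results, so neither depends on the sample size. The tighter precision of 0.02 that the protocol mentions for imbalanced outcomes would not help either: an interval of 0.88 to 0.92 is still half below 0.90.

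**3. Exact check for a yes/no test.** For a binary result, AUC = (sensitivity + specificity) / 2 and SE = ½ √[Se(1 − Se)/n₁ + Sp(1 − Sp)/n₀]. With Se = Sp = 0.90, 384 evaluable patients and a Wald interval, enumerating all binomial outcomes gives the table below. CT-positive prevalence is an assumption. The protocol's background section on mild head trauma cites CT abnormalities in 5% (GCS 15) and 30% (GCS 13), but the trial also counts previous lesions, so its prevalence may differ. The last column uses 0.85 only as an illustrative minimum.

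| CT-positive | n₁ / n₀ | SE | P(lower limit > 0.90) | P(estimate ≥ 0.90) | P(lower limit > 0.85) |
|---|---|---|---|---|---|
| 50% | 192 / 192 | 0.0153 | 4.2% | 52% | 88% |
| 30% | 115 / 269 | 0.0167 | 4.6% | 52% | 82% |
| 10% | 38 / 346 | 0.0256 | 8.6% | 52% | 53% |
| 5% | 19 / 365 | 0.0353 | 13.5% | 53% | 42% |

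The excess over 2.5% in the fourth column is undercoverage of the Wald interval in small groups and is not real power. A logit interval gives 1.8% at 50% CT-positive and 2.4% at 30%. Adding the 80% floors for observed sensitivity and specificity leaves the point-estimate column unchanged.

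**4. True AUC needed to demonstrate 0.90.** Solve p − 0.90 = (1.96 + 0.84) √[p(1 − p)/384] for 80% power: p ≈ 0.935. With the SE held at 0.0153, p ≈ 0.90 + 2.80 × 0.0153 = 0.943. At a true AUC of 0.935 the exact Wald calculation gives 77% at 192/192 but 46% at 38/346.

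**The case against.** The strongest reply is that this is an estimation study with loose wording. The sample size is explicitly a precision calculation and is arithmetically right. No null hypothesis, decision rule or power is stated, and how the interval is judged is commonly left to the SAP, which is not at hand. This is true as far as it goes, and no figure in the sample size section is wrong. But the conflict lies between a stated hypothesis and a stated sizing assumption, both in the protocol. An SAP could choose the interval or the point estimate, and neither choice is supported by the sizing.

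Three stronger readings are tempting and should not be drawn.

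- *A reader might infer that a device performing as the sponsor expects will fail.* The Expected Results section assumes reliability of 90% or more, and the section on prior clinical experience reports near-complete agreement with CT in 20 patients. So 0.90 may be the floor of the expectation. For precision it is also a cautious value, since the variance falls as the AUC rises. The statement holds only at the value used for sizing.
- *A reader might infer that the interim analyses inflate the chance of a false pass.* The protocol says only that "An interim analysis is planned for the respective cohorts of study patients when the thresholds of 150 and 300 patients enrolled" in each cohort. It does not say that the AUC threshold is judged then, that success may be declared or that a cohort may stop. Any inflation figure would need a rule that the protocol does not contain.
- *A reader might infer that a lower minimum such as 0.85 solves the problem with the present size.* The figure 0.85 appears nowhere in the protocol, and the table shows that power for it falls to about half or less at 10% CT-positive and below.

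**Conclusion.** The point holds as a mismatch between the Statistics section and the sample size section. At the sizing assumption, a true AUC of 0.90, the chance of putting the lower 95% limit above 0.90 is 2.5% nominally. With a Wald interval it is about 4% at an assumed 50% CT-positive, rising to about 14% at 5% through undercoverage alone. The chance that the point estimate reaches 0.90 is about one half. The nominal 2.5% and 50% do not depend on sample size or prevalence. They do depend on the true AUC being 0.90; a value near 0.935 or higher, with CT results close to balanced, would be needed for about 80% power.

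The precision calculation stands, and the finding does not show that the device is likely to fall short. The matter is worth correcting before results are known, because the primary claim as worded is not one that the design was sized to support.

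**What to change.** Reconcile the two sections by wording, leaving the number of patients as it is. Either:

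1. State that each cohort estimates AUC, sensitivity and specificity with 95% confidence intervals, and remove the language of proving or demonstrating at least 90%; or
2. Keep 0.90 as the expected AUC, have the sponsor set and justify a separate minimum below 0.90 that the lower 95% limit must exceed, and show the power by CT-positive prevalence.

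Under option 2, state that the criterion is judged once per cohort, at full enrolment, which also settles that the interim analyses do not test it.

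The cost is a less favourable headline claim. Option 1 has no other cost. Option 2 does not require more patients as a matter of wording, but the power table may show that the present size is inadequate: with 0.85 as an illustration, power is about 88%, 82%, 53% and 42% at 50%, 30%, 10% and 5% CT-positive. If low prevalence is expected in a cohort, option 1 is the safer description of what the current size can deliver.
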